7.5.1. Quantitative Serum Immunoglobulin

Testing for IgA, IgG and IgM levels will be performed by central laboratory.

7.5.2. Serum Immunofixation

Samples will be collected and sent to a central laboratory. Repetitive immunofixation on study is only required to confirm CR (conducted on the first observation that the subject has no detectable monoclonal protein) and then repeated every study visit until disease progression.

7.5.3. Serum Protein Electrophoresis (SPEP)

Sample(s) will be sent to a central laboratory to quantify the serum-M protein.

7.5.4. Radiographic Imaging

Pretreatment tumor assessment will be performed up to 42 days before the first dose of study drug. Lesions that have been irradiated cannot be included in the tumor assessment unless unequivocal tumor progression has been documented in these lesions after radiation therapy.

A CT scan (with contrast unless contraindicated) of the neck, chest, abdomen, and pelvis must be performed. Information on extranodal involvement will also be recorded.

In the case where CT with contrast is contraindicated, an alternative would be MRI of the abdomen and pelvis and CT of the chest without contrast.

NOTE: Positron emission tomography (PET)/CT hybrid scanners may be used to acquire the required CT images only if the CT produced by the scanner is of diagnostic quality, adheres to the specified slice thickness/scan parameters, and includes the use of intravenous (IV) contrast.

Additionally, the CT images must be separated from the PET data prior to submitting the data, and cannot be transmitted as fused PET/CT images.

If using a hybrid machine to acquire both PET and CT, the PET must be performed prior to the CT with IV contrast as to not compromise PET results.

If independent CT and PET scanners are used, and the subject is receiving both scans on the same day, the PET must be performed prior to the CT with IV contrast.

The same imaging method should be used for a given subject throughout the study. The same equipment should be utilized for all scans whenever possible. The same radiologist should be assigned to read all the scans for a given patient throughout the study as much as possible.

All subjects with presence of nodal and/or extranodal disease at Screening per central radiology review will require follow up CT scans of the neck, chest, abdomen, and pelvis every 16 weeks for the first 2 years and thereafter every 24 weeks, until disease progression is confirmed by the IRC (regardless of whether or not the patient remains on treatment). Follow up neck CT scans are only required for subjects with evidence of disease involvement in the neck region identified during Screening. In the event disease progression is suspected due to physical examination or laboratory test, a CT scan should be performed to evaluate nodal or extranodal progression regardless if the subject had nodal/extranodal disease at Screening.

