7.1.6. Physical Examination

The Screening, Week 1, Suspected PD, End-of-Treatment and Follow-Up physical examination will include, at a minimum, the general appearance of the subject, height (screening only) and weight, and examination of the skin, eyes, ears, nose, throat, lungs, heart, abdomen, extremities, musculoskeletal system, nervous system, and lymphatic system.

A limited symptom-directed physical examination will be required after Week 1 at time points specified in the Schedule of Assessments ([Appendix 1](#)).

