7.5.4.1. Radiographic Assessment

Progression of nodal and extranodal disease should be evaluated based on the revised criteria for malignant lymphoma described in the revised International Working Group for NHL ([Cheson 2007](#)). The spleen is considered nodal disease.

Up to 6 measurable lymph nodes (target lesions) should be considered if the long axis is more than 1.5 cm regardless of the short axis. If a lymph node has a long axis of 1.1 to 1.5 cm, it should only be considered abnormal if its short axis is more than 1.0 cm. Lymph nodes ≤ 1.0 cm x ≤ 1.0 cm will not be considered as abnormal for relapse or progressive disease. In addition, target lesions should be clearly measurable in at least 2 perpendicular dimensions and, if possible, they should be from disparate regions of the body when these areas are significantly involved. If additional lesions are present but are not included in the target lesion assessment, they can be added as non-target lesions followed throughout the study.

The longest cranial-caudal measurement of the spleen will be assessed at Screening and all subsequent timepoints (if applicable).

Nodal progression by imaging is defined as one of the following:

- Appearance of any new lesion more than 1.5 cm in any axis during or at the end of therapy, even if other lesions are decreasing in size.

- At least a 50% increase from nadir in the sum of product (SPD) of any previously involved nodes, or in a single involved node. To be considered progressive disease, a lymph node with a diameter of the short axis of less than 1.0cm must increase by $\geq 50\%$ and to a size of 1.5 x 1.5 cm or more than 1.5 cm in the long axis.
- At least a 50% increase in the longest diameter of any single previously identified node more than 1 cm in its short axis

Measurable extranodal disease should be assessed in a manner similar to that for nodal disease.

A central imaging service will be utilized to provide independent radiological assessments for independent response evaluation (Refer to [Section 10.10](#)). Central radiology review will be conducted throughout the study and the details of the central radiology review activities will be specified in a separate charter and the SAP.

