- ^g Subsequent Serum viscosity (after Screening) should be performed at the discretion of the treating physician in any subject with signs and symptoms suggesting a hyperviscosity syndrome.
- ^h Repetitive serum immunofixation on study is only required to confirm CR (conducted on the first observation that the subject has no detectable monoclonal protein) and then repeated every time until disease progression.
- ⁱ Pharmacokinetic samples will be drawn for all subjects according to the schedule in Section 7.4.1. Week 4 PK will only be required for Arm A and Arm B. Week 5 PK will only be required for Arm C.
- ^j These parameters will be used to assess possible IgM flare after initiating treatment for safety observations for Treatment Arm A and Arm B only.
- ^k CT scans of the neck, chest, abdomen, and pelvis should be obtained during Screening (up to 42 days before first dose) for each subject.
- ^l Follow-Up CT scans will be required at Weeks 17, 33, 49 65, 81, 97 and thereafter every 24 weeks for all subjects with measurable nodal/extranodal disease per central radiology review during Screening. Additional assessments may be performed if clinically indicated during the course of the study at any time.
- ^m CT scan at Suspected PD visit may be performed if clinically indicated as reason for progression.
- ⁿ Bone marrow aspirate and biopsy required at Screening, Weeks 49 and 97 (± 2 weeks) to confirm paraprotein changes, and at any time as determined necessary or to confirm a complete response if the subject has no detectable monoclonal protein, and if clinically indicated at disease progression or end-of-treatment visit. A portion of these samples may be used for biomarker assessments.
- ^o With Bone Marrow Aspirate prepare 4 smears, perform required assays at site and submit up to 10 mL aspirate to central lab
- ^p Biomarker sample: One 8.5 mL blood sample in Acid Citrate Dextrose (ACD) and one 10mL blood sample in Sodium Heparin will be collected for biomarker evaluations at the beginning of Week 1, Week 17, Week 33 and Week 49. Additional samples will also be obtained at the time of complete response assessment and at disease progression (or at End-of Treatment Visit for subjects who discontinue treatment without disease progression).
- ^q Portion of sample collected at Week 1 will be used for evaluation of genetic and molecular prognostic markers.

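### The imaging alternative for subjects who cannot have contrast CT omits the neck, so a site that follows it as written can leave cervical nodes without an imaging baseline

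*Protocol*

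**What the plan says.** The main requirement in Protocol Section 7.5.4 is: "A CT scan (with contrast unless contraindicated) of the neck, chest, abdomen, and pelvis must be performed". Appendix 1, footnote k, repeats the four regions with no exception: "CT scans of the neck, chest, abdomen, and pelvis should be obtained during Screening (up to 42 days before first dose) for each subject".

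For subjects in whom contrast CT is contraindicated, Section 7.5.4 then states that "an alternative would be MRI of the abdomen and pelvis and CT of the chest without contrast". The neck does not appear. The PET/CT route in the same section needs intravenous contrast, so it does not help these subjects. Section 8.2.1, which lists the Screening procedures, allows CT or another modality that Section 7.5.4 describes.

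Later imaging depends on what Screening finds:

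- Scheduled follow-up CT is for subjects with nodal or extranodal disease at Screening according to central radiology review (Section 7.5.4). Footnote l narrows this to measurable disease.
- For the neck in particular: "Follow up neck CT scans are only required for subjects with evidence of disease involvement in the neck region identified during Screening".
- On modality: "The same imaging method should be used for a given subject throughout the study".
- If examination or laboratory results raise suspicion of progression, "a CT scan should be performed to evaluate nodal or extranodal progression regardless if the subject had nodal/extranodal disease at Screening". The regions to be scanned are not listed.

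Section 7.5.4.1 counts this as nodal progression, without limit by region: "Appearance of any new lesion more than 1.5 cm in any axis during or at the end of therapy".

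**The concern.** The alternative looks like a full replacement for the four-region CT, yet it covers three regions. It spells out a non-contrast CT for the chest. If regions that can be scanned without contrast carried over unstated, the chest would not have needed naming either. A site can therefore reasonably conclude that the neck is not needed in these subjects.

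Three things are at stake, all for IRC-assessed endpoints. Under Appendix 4, partial and very good partial response need a reduction in any lymphadenopathy present at baseline, and complete response needs its resolution. Neck nodes that were never recorded drop out of that test. Entry to scheduled CT follow-up depends on the central reading of the Screening scans. And without a baseline, a neck node seen for the first time late in the study cannot be told apart from one present at entry. IRC-confirmed progression is a PFS event, ends study treatment (Section 9.2) and is a condition for crossover (Section 7.7.1), so a wrong call would matter for the subject as well as for the endpoint.

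**Working it through.** The plan has no figure of its own to reproduce on this point. The check compares the text and then sizes the problem on stated assumptions.

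**1. Regions covered.**

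| Source | Neck | Chest | Abdomen | Pelvis |
|---|---|---|---|---|
| Section 7.5.4, main requirement | CT | CT | CT | CT |
| Appendix 1, footnote k | CT | CT | CT | CT |
| Section 7.5.4, alternative | not named | CT, no contrast | MRI | MRI |
| Section 7.5.4, scheduled follow-up | only if neck disease found at Screening | CT | CT | CT |
| Section 7.5.4, suspected progression | regions not listed | regions not listed | regions not listed | regions not listed |

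**2. Two readings.** Under the first, the main requirement governs. Only the contrast is conditional, and a non-contrast neck CT is still due. Under the second, the alternative is the complete set for these subjects and Section 8.2.1 accepts it. The text admits both. The steps below apply only where a site acts on the second.

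**3. Could other data supply a neck baseline for the IRC?** The full physical examination at Screening includes the "musculoskeletal system, nervous system, and lymphatic system", so palpable nodes can be noted. But examination is not among the efficacy components listed in Section 7.5. Section 10.10 has the IRC work from central radiology and laboratory evaluations, and note 4 of Appendix 4 has lymph nodes evaluated by CT. At scheduled treatment visits after Week 1 only a limited symptom-directed examination is required (Section 7.1.6). Palpation can prompt a scan; it does not give a measured baseline.

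**4. Consequences under the second reading.**

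- *Response.* Change in neck nodes cannot be measured. If the neck is the only nodal site and the spleen is not enlarged, partial response rests on IgM alone. If there are nodes elsewhere or an enlarged spleen, those are still assessed.
- *Scheduled scans.* A subject is left out only if central radiology finds nothing in chest, abdomen or pelvis. Section 7.5.4.1 counts the spleen as nodal disease, and extranodal disease also qualifies. Losing all scheduled scans therefore needs neck-only disease.
- *Progression.* A scan at suspected progression may be the first to include the neck. An old node larger than 1.5 cm could then be taken for a new lesion. Appendix 4 requires an IgM rise to be confirmed only when IgM is the sole criterion, so an apparently new node could also remove that safeguard.

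**5. Size.** The documents give neither the share of subjects who cannot have contrast nor the share with cervical nodes. Both rates here are assumptions.

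- Randomized subjects: 150 (Protocol Section 10.5; SAP Section 1.1).
- Cannot have contrast, assumed 5% to 15%: 150 × 0.05 = 7.5; 150 × 0.15 = 22.5.
- Of these, cervical nodes, assumed 10% to 30%: 7.5 × 0.10 = 0.75; 22.5 × 0.30 = 6.75.

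That is about 1 to 7 subjects. For those rates it is an upper figure, because it supposes that every site concerned uses the alternative and skips the neck. Subjects with neck-only disease, and any misread new lesions, are subsets that the documents do not allow to be sized.

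**The case against.** The strongest reply is that the neck was never waived. The sentence before the alternative already deals with contraindication: contrast may be omitted, but all four regions must be scanned. Footnote k makes no exception, and the alternative is worded as an option. On that reading a non-contrast neck CT remains due, and the alternative merely fails to say so. This stands as a fair reading, probably the better one. It does not remove the ambiguity, because the alternative names the chest but not the neck and Section 8.2.1 points sites to it.

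The second reply is that safeguards remain. Neck involvement is not confined to imaging evidence in the follow-up rule, sites of lymphadenopathy are reported to central pathology (Section 7.3.2), and a CT is called for at suspected progression whatever Screening showed. The consistency-of-method rule concerns modality and does not bar adding the neck. These points stand, with one limit: entry to scheduled CT follow-up turns on central radiology, which cannot report a region it did not receive.

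A reader might infer more: that every subject who cannot have contrast lacks a neck baseline, that neck progression cannot be judged in them at all, or that an old node would become a false PFS event. The documents do not support this. The first overlooks the mandatory four-region sentence and footnote k. The second overlooks the scan at suspected progression and the new-lesion rule. The third assumes how the IRC would treat a region never imaged before, which neither the protocol nor the SAP states and which the charters may cover.

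**Conclusion.** The omission is real and the correction worthwhile, but the point is minor. The alternative covers three of the four required regions, and the text lets a site treat it as sufficient. Where that happens, nodal response and new-lesion calls in the neck have no imaging baseline, and subjects with neck-only disease miss scheduled CT follow-up.

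The number involved is likely small: at most about 1 to 7 of 150 on the assumed rates. The effect on PFS is limited further because Appendix 4 lets progression be met by IgM and other criteria. No effect on power or the treatment comparison is shown. The conclusion assumes that some sites follow the alternative literally and that the IRC and radiology charters do not already require the neck.

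**What to change.** Name the neck in the Section 7.5.4 alternative. Either extend the non-contrast CT from the chest to the neck and chest, or add MRI of the neck. Either version covers the four regions that the same section and footnote k require, and Section 8.2.1 then follows without change. The sponsor should also check that the IRC and central radiology charters agree.

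The first version costs two added words. No region is added beyond those already required of every subject at Screening. The change touches measurement only; it affects no treatment rule, sample size or analysis method.

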7.5.4.1. Radiographic Assessment

Progression of nodal and extranodal disease should be evaluated based on the revised criteria for malignant lymphoma described in the revised International Working Group for NHL ([Cheson 2007](#)). The spleen is considered nodal disease.

Up to 6 measurable lymph nodes (target lesions) should be considered if the long axis is more than 1.5 cm regardless of the short axis. If a lymph node has a long axis of 1.1 to 1.5 cm, it should only be considered abnormal if its short axis is more than 1.0 cm. Lymph nodes ≤ 1.0 cm x ≤ 1.0 cm will not be considered as abnormal for relapse or progressive disease. In addition, target lesions should be clearly measurable in at least 2 perpendicular dimensions and, if possible, they should be from disparate regions of the body when these areas are significantly involved. If additional lesions are present but are not included in the target lesion assessment, they can be added as non-target lesions followed throughout the study.

The longest cranial-caudal measurement of the spleen will be assessed at Screening and all subsequent timepoints (if applicable).

Nodal progression by imaging is defined as one of the following:

- Appearance of any new lesion more than 1.5 cm in any axis during or at the end of therapy, even if other lesions are decreasing in size.

- At least a 50% increase from nadir in the sum of product (SPD) of any previously involved nodes, or in a single involved node. To be considered progressive disease, a lymph node with a diameter of the short axis of less than 1.0cm must increase by $\geq 50\%$ and to a size of 1.5 x 1.5 cm or more than 1.5 cm in the long axis.
- At least a 50% increase in the longest diameter of any single previously identified node more than 1 cm in its short axis

Measurable extranodal disease should be assessed in a manner similar to that for nodal disease.

A central imaging service will be utilized to provide independent radiological assessments for independent response evaluation (Refer to [Section 10.10](#)). Central radiology review will be conducted throughout the study and the details of the central radiology review activities will be specified in a separate charter and the SAP.

To ensure the required subsequent CT scans are performed per protocol, the presence of nodal/extranodal disease per central radiology review will be communicated to the site. However, no further details (eg, measurements or identified target/non-target lesions) will be reported back to the site.

7.6. Sample Collection and Handling

The actual dates and times of sample collection must be recorded in source documents for transcription to the eCRF or laboratory requisition form. Refer to the Schedule of Assessments ([Appendix 1](#)) for the timing and frequency of all sample collections.

Instructions for the collection, handling, and shipment of samples are found in the Laboratory Manual.

7.7. Treatment with Ibrutinib for Subjects on Control Arm (Arm B) Following IRC-Confirmed Disease Progression

Subjects on the trial who have documented IRC confirmed disease progression and symptomatic disease meeting criteria for requiring treatment may be eligible to receive next-line therapy with ibrutinib. A request for next-line therapy with ibrutinib must be submitted to the Sponsor's designee who will evaluate the request based on the criteria listed in [Section 7.7.1](#). Local labs can be used to determine appropriateness for start of next-line ibrutinib.

Next-line treatment with ibrutinib can be continued until disease progression as determined by the Investigator, or until they meet the following criteria for withdrawal in [Section 9](#).

7.7.1. Criteria for Next-line Ibrutinib Therapy

1. IRC confirmed disease progression and Sponsor approval.

2. Symptomatic disease meeting at least 1 of the recommendations from the Second International Workshop on Waldenström's Macroglobulinemia for requiring treatment ([Section 4.1](#). Inclusion criteria #4).
3. Compliant with the main study protocol procedures and no subsequent WM/anti-cancer therapy prior to IRC confirmed disease progression since discontinuing treatment on Arm B.
4. ECOG Performance Status of ≤ 2 ([Appendix 2](#)).
5. Platelet count $>50,000$ cells/mm³ and absolute neutrophil count >750 cells/mm³.
6. No uncontrolled active systemic fungal, bacterial, viral, or other infection (defined as exhibiting ongoing signs/symptoms related to the infection and without improvement, despite appropriate antibiotics or other treatment).
7. No currently active clinically significant cardiovascular disease such as uncontrolled arrhythmia, congestive heart failure, any Class 3 or 4 cardiac disease as defined by the New York Heart Association Functional Classification ([Appendix 5](#)), or history of myocardial infarction within 6 months prior to first dose with study drug.
8. Female subjects who are of non-reproductive potential (ie, post-menopausal by history - no menses for ≥ 2 year; OR history of hysterectomy; OR history of bilateral tubal ligation; OR history of bilateral oophorectomy). Female subjects of reproductive potential must have a negative pregnancy test upon study entry.
9. Male and female subjects of reproductive potential who agree to use highly effective methods of birth control (eg, condoms, implants, injectables, combined oral contraceptives, some intrauterine devices [IUDs], complete abstinence^b, or sterilized partner) during the period of therapy and for 30 days after the last dose of study drug and 90 days (males) after the last dose of study drug.

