1.3.2. Safety Pharmacology and Toxicology

In safety pharmacology assessments, no treatment-related effects were observed in the central nervous system or respiratory system in rats at any dose tested. Further, no treatment-related corrected QT interval (QTc) prolongation effect was observed at any tested dose in a cardiovascular study using telemetry-monitored dogs.

Based on data from rat and dog including general toxicity studies up to 13 weeks duration, the greatest potential for human toxicity with ibrutinib is predicted to be in lymphoid tissues (lymphoid depletion) and in the gastrointestinal tract (soft feces/diarrhea with or without inflammation). Additional toxicity findings seen in only one species with no observed human

correlate in clinical studies to date include pancreatic acinar cell atrophy (rat), minimally decreased trabecular and cortical bone (rat) and corneal dystrophy (dog).

In vitro and in vivo genetic toxicity studies showed that ibrutinib is not genotoxic. In a rat embryo-fetal toxicity study, ibrutinib administration was associated with fetal loss and malformations (teratogenicity) at ibrutinib doses that result in approximately ≥ 8 times and 20 times the exposure (AUC) in subjects administered the dose of 420 mg daily, respectively.

For the most comprehensive nonclinical and clinical information regarding ibrutinib, please refer to the current version of the Investigator's Brochure.

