7.2.8. Pregnancy Test

Serum pregnancy test will be required at Screening by local laboratory only for women of reproductive potential. A urine pregnancy test will also be performed on Day 1 prior to first dose. If positive, pregnancy must be ruled out by ultrasound to be eligible. This test may be performed more frequently if required by local regulatory authorities.

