7.7.2. Next-line Ibrutinib Therapy Treatment Phase

Refer to the next-line ibrutinib therapy Schedule of Assessments ([Appendix 9](#)) for a complete list of procedures to be performed at each scheduled study visit.

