9.2. Withdrawal from Study Treatment

Study treatment will be discontinued in the event of any of the following events:

- Confirmed progressive disease by IRC
- Unacceptable toxicity: an intercurrent illness or adverse event that prevents further ibrutinib administration
- Withdrawal of consent for treatment by subject
- Investigator decision (such as chronic noncompliance, significant protocol deviation, or best interest of the subject)

- Study termination by Sponsor
- Subject becomes pregnant

All subjects, regardless of reason for discontinuation of study treatment will undergo an End-of-Treatment Visit and be followed for progression and survival.

The Investigator should notify the Sponsor within 24 hours if a subject discontinues ibrutinib treatment due to disease progression and should provide documentation of disease progression for review by the Sponsor's Medical Monitor. If a subject shows signs of disease progression on physical examination or laboratory assessment, the subject may continue study treatment until disease progression is confirmed by IRC. These subjects should stay in the study to be followed for survival.

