11.3.5. Pregnancy

Before study enrollment, subjects must agree to take appropriate measures to avoid pregnancy including the use of contraception or complete abstinence in accordance with the local approved rituximab label and ibrutinib guidance. However, should a pregnancy occur in a female study subject, consent to provide follow-up information regarding the outcome of the pregnancy and the health of the infant until 30 days old will be requested.

A female subject must immediately inform the Investigator if she becomes pregnant from the time of consent to 30 days after the last dose of ibrutinib/placebo or 18 months after the last dose of rituximab, whichever occurs later. A male subject must immediately inform the Investigator if his partner becomes pregnant from the time of consent to 90 days after the last dose of ibrutinib/placebo or 18 months after the last dose of rituximab, whichever occurs later. Any female subjects receiving study drug(s) who become pregnant must immediately discontinue study drug. The Investigator should counsel the subject, discussing any risks of continuing the pregnancy and any possible effects on the fetus.

Although pregnancy itself is not regarded as an adverse event, the outcome will need to be documented. Any pregnancy occurring in a subject from the time of consent to 30 days after the last dose of ibrutinib/placebo or 18 months after the last dose of rituximab, whichever occurs later, must be reported. Any pregnancy occurring in a subject's partner from the time of consent to 90 days after the last dose of ibrutinib/placebo or 18 months after the last dose of rituximab, whichever occurs later, must be reported. Any occurrence of pregnancy must be recorded on the Pregnancy Report Form Part I and sent via email or fax to Pharmacyclics Drug Safety, or designee, within 24 hours of learning of the event. All pregnancies will be followed for outcome, which is defined as elective termination of the pregnancy, miscarriage, or delivery of the fetus. For pregnancies with an outcome of live birth, the newborn infant will be followed until 30 days old by completing the Pregnancy Report Form Part II. Any congenital anomaly/birth defect noted in the infant must be reported as a serious adverse event.

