HI12	I feel weak all over.....	0	1	2	3	4
An1	I feel listless (“washed out”).....	0	1	2	3	4
An2	I feel tired.....	0	1	2	3	4
An3	I have trouble starting things because I am tired	0	1	2	3	4
An4	I have trouble finishing things because I am tired ..	0	1	2	3	4
An5	I have energy	0	1	2	3	4
An6	I have trouble walking	0	1	2	3	4
An7	I am able to do my usual activities	0	1	2	3	4
An8	I need to sleep during the day	0	1	2	3	4
An9	I feel lightheaded (dizzy)	0	1	2	3	4
An10	I get headaches.....	0	1	2	3	4
B1	I have been short of breath.....	0	1	2	3	4
An11	I have pain in my chest	0	1	2	3	4
An12	I am too tired to eat	0	1	2	3	4
BL4	I am interested in sex	0	1	2	3	4
An13	I am motivated to do my usual activities	0	1	2	3	4
An14	I need help doing my usual activities.....	0	1	2	3	4
An15	I am frustrated by being too tired to do the things I want to do	0	1	2	3	4
An16	I have to limit my social activity because I am tired	0	1	2	3	4

Appendix 9. Schedule of Assessments for Subjects Treated with Placebo in Combination with Rituximab and Documented IRC confirmed Progression who Elect to Receive Next-line Ibrutinib Therapy

Study Weeks	Assessment for Eligibility for Next-line Ibrutinib Therapy	Treatment Phase			Follow-up Phase
		Every 4 weeks for 16 weeks	Every 8 weeks thereafter until PD	End-of-Treatment Visit	Follow-up (Every 12 weeks)
Study Windows		±3 d	±3 d	30 (±3 d)	±7 d
Study Drug Administration					
Ibrutinib 420 mg per day PO		Continuous Daily Dosing			
Procedures					
IRC-confirmed PD ^a	x				
Sponsor's Designee approval	x				
Concomitant medications	x	x	x	x	
Adverse events		x	x	x	
Physical examination, vital signs, ECOG	x ^b	x	x	x	
Hematology ^c	x ^b	x	x	x	
Serum chemistry ^c	x ^b	x	x	x	
Serum immunoglobulins ^c (IgM)	x ^b	x	x	x	
Investigator assessment of response and for progression		x	x		
Survival status					x
Subsequent anticancer therapies					x

d=day; ECOG=Eastern Cooperative Oncology Group; IRC=Independent Review Committee; PD=progressive disease; PO=oral; qd=once daily

^a Documentation from IRC required for Sponsor's designee approval to receive next-line ibrutinib therapy

^b Assessments for next-line ibrutinib should be performed ±10 days from unblinding

^c Assessments performed by local laboratory

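### No pregnancy test is scheduled before Arm B subjects start next-line ibrutinib, and the infarction look-back in the same criteria can run from either of two dates

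*Protocol*

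**What the plan says.** Criterion 8 of Protocol 7.7.1 reads "Female subjects of reproductive potential must have a negative pregnancy test upon study entry". Inclusion criterion 10 in 4.1.1 contains the same sentence, where it refers to joining the trial.

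Section 7.2.8 sets the testing schedule. A local serum test is done at Screening, and "A urine pregnancy test will also be performed on Day 1 prior to first dose". More tests are allowed for only where local regulators ask for them. Appendix 1, footnote f, agrees.

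Section 7.7.2 sends the reader to Appendix 9 "for a complete list of procedures to be performed at each scheduled study visit". Appendix 9 has an eligibility column, and its footnote b adds that "Assessments for next-line ibrutinib should be performed ±10 days from unblinding". The table has no pregnancy-test row, either at eligibility or later.

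Criterion 7 of 7.7.1 bars currently active significant cardiac disease and also a "history of myocardial infarction within 6 months prior to first dose with study drug". Section 5.3.1 defines study drug to cover placebo as well as ibrutinib. Appendix 9 lists next-line ibrutinib under its study drug administration heading.

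**The concern.** For an Arm B subject, crossover is the first exposure to ibrutinib. At randomization the protocol requires a negative test immediately before the first dose. At crossover, when exposure actually begins for these women, it requires nothing new. A pregnancy that began during the placebo phase and has not been noticed would not be picked up.

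Section 1.3.2 gives the reason for caution: in rats, "ibrutinib administration was associated with fetal loss and malformations (teratogenicity", at about 8 or more and 20 times, respectively, the exposure of the 420 mg daily dose. The sponsor's designee, who judges each request against 7.7.1, is not assured of a current pregnancy result and has two possible dates from which to count the infarction window.

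**Working it through.** The plan states no figure on this point, so the check is mainly a comparison of texts, plus one count and one illustration.

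**Required pregnancy tests (7.2.8; Appendix 1, footnote f).** Serum at Screening and urine on Day 1 give 2 tests. Both precede the first randomized dose.

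**Items marked in the Appendix 9 eligibility column:**
1. IRC-confirmed progression
2. designee approval
3. concomitant medications
4. physical examination, vital signs and ECOG
5. hematology
6. serum chemistry
7. serum IgM

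That is 7 items, of which 0 are pregnancy tests. Items 4 to 7 carry footnote b, so the plan asks for fresh results on these near unblinding but not for pregnancy.

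**Safeguards elsewhere.**
- Section 9.2, which 7.7 applies to crossover subjects, lists "Subject becomes pregnant" as a reason to stop treatment. Section 11.3.5 says "Any female subjects receiving study drug(s) who become pregnant must immediately discontinue study drug". Both act on a pregnancy that is already known, and neither calls for a test.
- Criterion 9 of 7.7.1 requires contraception during therapy and for a period afterwards. It does not establish that a woman is not pregnant when therapy starts.
- Main-study criterion 11 ends the contraception requirement for women 30 days after the last dose of study drug. Criterion 3 of 7.7.1 allows for subjects who stopped Arm B treatment before progression, and 8.4.1 follows them every 12 weeks. Such a woman could be past the 30 days at crossover. Section 11.3.5 also points to the rituximab label, which may lengthen the obligation but adds no test.
- The main-study exclusion of pregnant or lactating women (4.1.2, no. 21) is not repeated in 7.7.1.

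**How old the last test could be (illustration only).** Protocol 10.5 assumes exponential PFS with a 15-month control median, so S(t) = 2^(−t/15).
- S(6) = 2^(−0.4) = 0.758, so about 76% of Arm B would still be event-free at 6 months.
- S(36) = 2^(−2.4) = 0.189, taking 36 months from the roughly 3 years of follow-up after the last randomization in 3.1.
- Share of the first 36 months' events that fall after month 6: (0.758 − 0.189) / (1 − 0.189) = 0.569 / 0.811 = 0.70.

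If crossover times track these events, about 70% of crossovers would come more than 6 months after the last required test. PFS events include deaths, which do not lead to crossover, and the further need for symptomatic disease and approval can only lengthen the delay.

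**Criterion 7, two readings.**
- From the Day 1 placebo dose: the window nearly duplicates exclusion 18 in 4.1.2, which looks back 6 months from randomization, because 5.1 has dosing follow randomization within 72 hours. An infarction during the placebo phase, without currently active disease, would not be excluded.
- From the first next-line ibrutinib dose: that infarction is excluded if it fell within the preceding 6 months.

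**The case against.** The strongest reply is that criterion 8 sits in a list applied at the time of a crossover request, so the sensible reading is entry to the next-line phase. Read as original enrolment it does no work, since every Arm B subject has already met inclusion criterion 10. On the sensible reading a test is required and the fault is one copied phrase. That is probably the intent, but the text does not say it, and Appendix 9 would then omit a laboratory test that its own criteria demand. Either reading needs an edit.

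A second reply is that other 7.7.1 criteria also lack an Appendix 9 row (symptomatic disease, infection, infarction history, contraception), and that the completeness wording in 7.7.2 appears under a treatment-phase heading. This has some force. However, the unlisted items are matters of history or clinical judgment. The criteria that need a measurement, blood counts and ECOG, do have rows. No other section lists the eligibility procedures.

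Third, 7.7 permits local laboratories for judging readiness to start, so a site may supply a pregnancy result, and local rules may require one. That is true, but the protocol does not require it.

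Fourth, women in Arm A have no scheduled repeat tests after Day 1 either, so the trial relies throughout on contraception and prompt reporting. That is also true, but Arm A women are tested immediately before their first ibrutinib dose, and Arm B women who cross over are not.

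Finally, numbers are small: Arm B has about 75 subjects, only some will cross over, and median age in the earlier Phase 2 study in this disease was 63 years (1.6.2). This stands, and it limits the weight of the point.

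**Conclusion.** The concern holds. As written, the plan assures no current pregnancy result before first ibrutinib exposure in Arm B: 2 required tests, both before randomized dosing, and 0 of 7 eligibility items at crossover. The infarction anchor is a secondary drafting ambiguity. The next-line dose is probably meant, and currently active cardiac disease is barred on either reading.

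The number of subjects at risk cannot be computed, because the documents give neither the number of women of reproductive potential nor the number of infarctions. Both are assumed to be small. The 70% figure depends on the protocol's own exponential assumption and serves only to show that the gap is long. The primary PFS analysis is unaffected, because crossover follows IRC-confirmed progression. This is a patient-safety correction worth making in the next amendment.

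**What to change.** - In 7.7.1, anchor criterion 8 (pregnancy test) and criterion 7 (infarction look-back) to the period before the first dose of next-line ibrutinib.
- Add a pregnancy test for women of reproductive potential to the Appendix 9 eligibility column.
- Mention that test in 7.2.8 so that the testing schedule is complete in one place.

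The cost is wording in two criteria, one table row and a cross-reference, plus one inexpensive test, of a kind the trial already uses, in probably few women.
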